## 1 Introduction

The prevalence of Atrial Fibrillation (AF) in the Western world is high and increasing, from 0.9% to 24.2% in men over 85 years of age. These estimates are in line with data related to the United States, which indicates that the number of people with AF is expected to double by 2050.

AF ablation is now considered a secondary therapeutic line and can sometimes be used as primary therapy before the failure of any antiarrhythmic drug (AAD). The most common approach to AF ablation is based on isolation of the Pulmonary Veins (PVI), however, several alternative approaches are being used and studied (e.g. lines, fractional complex electrograms (CFE), rotors, epicardial approach). Radio frequency (RF) is predominantly used, with 3D mapping for both anatomical and electrical mapping.

St. Jude Medical (SJM) has a broad portfolio of products that can be used during atrial fibrillation (AF) ablation and recently expanded its portfolio with the new FlexAbility ablation catheters, which have enhanced handling capability and innovative irrigation, and TactiCath, which has a contact sensor.

Many studies approach the treatment of AF from a clinical perspective (see bibliography of 6-9). This registry aims to collect a large number of real cases focusing on the synergy between the various tools and investigate their impact on the effectiveness of the procedure and clinically in Brazil.

The results obtained will support the Brazilian medical society for

---

 Krijthe BP, Kunst The Benjamin EJ, Lip GYH, Franco OH, Hofman A, et al. Projections on the number of individuals with atrial fibrillation In fashion the European Union, from 2000 to 2060. Eur Heart J. 2013 Sep;34(35):2746–51.

 Kuck K-H, Reddy VY, Schmidt B, Natale The Neuzil P, Saoudi N, Et Al. A Novel Radiofrequency Ablation catheter using contact force Sensing: Toccata study. Heart Rhythm Off J Heart Rhythm Soc. 2012 Jan;9(1):18–23

recommendations of optimal techniques, evaluate overall costs, provide feedback for the development and creation of new tools, create data in support of randomized clinical trial designs, and provide information for choosing the appropriate tool within the various options.

1111111917652

## 2 Registry Delineation

### 2.1 Purpose

The purpose of this registry is to evaluate the performance and clinical efficacy of the combination of SJM mapping and ablation products in the treatment of atrial fibrillation (AF) in Brazil.

### 2.2 Goals

- Ensure patient safety as part of after-sales surveillance.
- Evaluate the combination of SJM products during the procedures.
- Assess the learning curve with a combination of SJM products.
- Collect feedback from users of SJM products

### 2.3 Type of Research

Post-commercial, national, multicenter, prospective and observational single-arm.

This registry will be conducted in approximately 25 centers around Brazil, seeking to include the greatest possible regional diversity.

### 2.4 Public to be registered

All patients who have indication for ablation of atrial fibrillation and who are willing to provide a written consent form, except pregnant women, may be included in this registry.

[REDACTED]

[REDACTED]

[REDACTED]

[REDACTED]

[REDACTED]

[REDACTED]

[REDACTED]

[REDACTED]

## 2.5 Products/Devices used

In order to ensure a minimum level of uniformity and to allow the comparison of acute and long-term efficacy as well as the efficiency of the procedure according to the technique used, a combination of 2 types of devices from the predetermined list should be used to qualify in this registry.

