### List of products/devices that should be used in this registration:

[figure not shown]
Combination of at least 2 devices:

- Ablation Catheter: TactiCath or FlexAbility
- Sheathed access: Agilis NxT or Swartz Braided
- Diagnostic catheter: Inquiry Afocus II DL, Optima or Reflexion Spiral

In the case of mapping, EnSite Velocity will need to be used.

Only commercially available SJM products should be used in this registration. The manuals provided should be consulted. New models that are made available in the market can be used once they are available, have ANVISA registration and approved for commercialization.

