### 3.2.1 Recruitment & Informed Consent Process

The investigator is responsible for screening for this Registry and obtaining the Informed Consent Form (ICF) from the patient, as applicable in accordance with local regulations. Obtaining the Informed Consent Form is mandatory for all patients (or their legal representatives) prior to participation in the investigation. The process of obtaining the TCLE must comply with the latest version of the Declaration of Helsinki, ISO 14155 and all applicable regulations. The principal investigator will conduct the consent process. This process will include a verbal discussion with the patient about all aspects of the clinical investigation that are relevant to their decision to participate in the study. It is crucial that this discussion is documented (patient hospital records).

The patient will be provided with a Free and Informed Consent Form written in a language that is understandable to the patient and that has been approved by the Ethics Committee. The patient will be given sufficient time to consider participation and ask questions if necessary.

In order to avoid any kind of undue influence, or inducement of the patient to participate, the sponsor requests the investigator to sign the Informed Consent Form only after the patient has signed and dated the document and therefore has voluntarily decided to participate.

The informed consent of a patient should always be dated and signed personally by the patient and the investigator responsible for conducting the informed consent process. It is crucial that the signature of the ICF is documented in the source documents (hospital records of the patient).

One copy of the original ICF must be kept on file by the investigator and a second signed original copy is provided to the research participant (responsibility of the investigator). The patient's legal rights will not be waived, nor will they appear to be unenforced. Native non-technical language will be used, understandable to the patient. New important information that becomes available during registration will need to be

provided in writing to new and existing patients. If relevant, all affected patients should confirm

Page 11 from 21

their participation in the study by providing their written informed consent.

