### 3.2.3 Ablation Procedure

- Products/Devices used;
- Ablation Parameters;
- Definition of ablation success and outcome;
- *User feedback* (Combination of products chosen, product handling, ease of use in combination with other equipment);
- Number, experience and type of service;
- Definition of the standard of care (follow-up procedures and occurrences).

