### 3.2.5 Serious cardiovascular adverse events

An adverse event should be reported in this registry when the event is considered to be of cardiovascular origin and has the potential to lead to:

-Death

- A serious deterioration of the patient's health , which may result in:

- A life-threatening disease or condition

- In: permanent capacity of a body structure or a bodily function;

- Prolonged hospitalization

- Medical or surgical intervention to prevent life-threatening disease or injury

- Malignant tumor

- Fetal distress, fetal death, or a congenital abnormality or defect

Planned hospitalization for a pre-existing condition is not considered a serious adverse event.

Cardiovascular serious adverse events (CAEs) include, but are not limited to, the following:

abnormal ECG, angina (chest pain), arrhythmia, fistula, complete heart block, coronary artery injury, cardiac perforation, thromboembolism, fluid overload, damage to components of the ICD or implantable pacemaker, morte, displacement of implantable defibrillator, and endocarditis, exacerbation of pre-existing atrial fibrillation, heart failure, arterial hypertension, AV block, esophageal fistula, myocardial infarction, obstruction/perforation/damage of the vascular system, palpitations, cardiac effusion/tamponade, pericardial effusion without tamponade, pericarditis, pulmonary vein dissection,

pulmonary vein stenosis, pulmonary vein thrombus, complete heart block, valvular damage, or ventricular arrhythmia insufficiency requiring defibrillation.

Procedure for the evaluation, registration and notification of EAGs

Cardiovascular EAGs should be reported following local regulation. All cardiovascular EAGs between patient recruitment and the end of registration must be reported to the sponsor and local Ethics Committees in accordance with local regulations.

In the event that an EAG occurs, complete and submit an Adverse Event to St. Jude Medical.

Additional information may be requested, if necessary, by Sponsor in order to report EAGs to regulatory authorities. The investigator must notify the Ethics Committee, if applicable, in accordance with national and local laws and regulations.

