3.2.6 Death

All patient deaths that occur during this registry must be reported to SJM within 72 hours of the center becoming aware of the fact. An Adverse Events form must be completed for all deaths at all centers.

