3.2.8 Exclusions

Every reasonable effort should be made to keep the patient on the Registry. If a patient completes their participation in the Registry, the future management of the patient will not be

altered by this decision, whether voluntary or not. If a patient drops out and completes participation in the Registry, document the information in the clinical exclusion form (CRF) as soon as possible.

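### Qualification depends on two listed device types being used, which is settled only during the procedure, and the plan does not say how started procedures that miss the condition are counted

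*Combined protocol and SAP*

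**What the plan says.** **Entry.** The visible part of Section 2.4 admits "All patients who have indication for ablation of atrial fibrillation and who are willing to provide a written consent form", apart from pregnant women. It sets no device condition.

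**Device condition.** Section 2.5 adds that "a combination of 2 types of devices from the predetermined list should be used to qualify in this registry". The product list that follows asks for "Combination of at least 2 devices" from three categories: ablation catheter, sheath and diagnostic catheter. No category is compulsory. The list also limits the registry to the sponsor's commercially available products.

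**Timing.** Section 3.2.1 states: "Obtaining the Informed Consent Form is mandatory for all patients (or their legal representatives) prior to participation in the investigation".

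**Safety reporting.** Section 3.2.5 states: "All cardiovascular EAGs between patient recruitment and the end of registration must be reported to the sponsor" (EAGs are serious adverse events). Section 3.2.6 states: "All patient deaths that occur during this registry must be reported to SJM within 72 hours". Neither depends on which devices were used.

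**Retention and deviations.** Section 3.2.8 opens with "Every reasonable effort should be made to keep the patient on the Registry" and contains no device-based exclusion. Section 3.2.7 treats any departure from the protocol as a deviation to be reported to the sponsor.

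**Analysis.** Section 6 plans descriptive comparisons by the combination of devices used, in up to 400 patients, a number it says was not calculated. It names no analysis population or denominator. Acute success appears in Section 3.2.3 only as a data item, "Definition of ablation success and outcome".

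**The concern.** A condition settled during the procedure, after consent, selects patients on something that can itself follow from a complication or from poor device handling. Two kinds of case are exposed:

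- a procedure stopped when only one listed type, for example the sheath, has been used;
- a procedure moved to unlisted products so that fewer than two listed types remain in use.

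Such cases bear directly on the goals in Section 2.2, which include patient safety, evaluation of the product combination and the learning curve. If they are left out and do worse than the rest, acute success looks better than it was. The serious-event rate looks lower if it is computed on qualifying patients only. The effect could differ between combinations, which are what Section 6 means to compare. Recruiting more patients does not remove a bias of this kind.

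**Working it through.** **Step 1. Who misses the condition.** Reading Section 2.5 with the product list:

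| Situation | Two listed types used? |
|---|---|
| Stopped with only a listed sheath used | No |
| Stopped before ablation, listed sheath and listed diagnostic catheter used | Yes |
| Switched from one listed product to another in the same category, second category also listed | Yes |
| Ablation catheter replaced by an unlisted one, listed sheath and diagnostic catheter in use | Yes |
| Only two listed categories planned, one replaced by an unlisted product | No, unless a device tried and abandoned counts as used |

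The exposed group is therefore narrower than all aborted or switched procedures.

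**Step 2. The plan's own figure.** There is nothing to reproduce. Section 6 says the 400 was not calculated, and the documents give no event rate, success rate, or share of procedures aborted or switched. Every rate below is an assumption.

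**Step 3. Formula.** Let f be the share of started procedures that miss the condition, k the rate in qualifying cases and d the rate in the others.

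Rate over all started procedures = (1 − f) × k + f × d

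Bias of the qualifying-only rate = k − [(1 − f) × k + f × d] = f × (k − d)

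The bias is zero when d = k, and its sign depends on which is larger.

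**Step 4. Serious events**, assuming k = 4%, if the denominator is restricted to qualifying patients. Rate over all started procedures:

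| f | d = 25% | d = 50% | d = 75% |
|---|---|---|---|
| 1% | 4.21% | 4.46% | 4.71% |
| 2% | 4.42% | 4.92% | 5.42% |
| 3% | 4.63% | 5.38% | 6.13% |

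- Lowest cell: 0.99 × 4% + 0.01 × 25% = 4.21%. Relative understatement: 1 − 4.00/4.21 = 5%.
- Highest cell: 0.97 × 4% + 0.03 × 75% = 6.13%. Relative understatement: 1 − 4.00/6.13 = 35%.
- Middle cell: 400 × 0.02 = 8 non-qualifying cases, 8 × 0.5 = 4 events not counted.
- With a milder d = 10%, the understatement is f × 6 points: 0.06 at f = 1% and 0.18 at f = 3%.

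**Step 5. Acute success**, assuming k = 95%:

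- d = 50%: overstatement f × 45 points, so 0.45 at f = 1% and 1.35 at f = 3%.
- d = 0%: overstatement f × 95 points, so 0.95 at f = 1% and 2.85 at f = 3%. The figure over all started procedures is then 94.05% to 92.15%.

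**Step 6. Against sampling error at n = 400** (95% half-width = 1.96 × √[p(1 − p)/400]):

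- p = 4%: 1.96 × √(0.04 × 0.96/400) = 1.9 points.
- p = 95%: 1.96 × √(0.95 × 0.05/400) = 2.1 points.

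In the Step 4 table only the highest cell, a bias of 2.13 points, exceeds its half-width. The middle cell's 0.92 points is about half of it. For acute success, 2.85 points exceeds 2.1, while 1.35 does not.

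**The case against.** A reader might infer that aborted and switched procedures are removed from the registry, and that safety and acute success are both biased favourably as a result. The documents do not support that, for these reasons:

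- **No removal rule is written.** Under Sections 3.2.7 and 3.2.8, a consented patient who misses the device condition could be kept and recorded as a deviation. This stands: exclusion is a consequence of applying Section 2.5 literally, not a stated procedure.
- **The wording can be read as intended equipment.** This is possible, particularly in translated text. Actual use is the more natural reading, and Section 6 also compares by devices used. If intention was meant, the sentence needs correcting.
- **Many aborted or switched cases still qualify.** This stands (Step 1).
- **Serious events and deaths are reportable without a device condition.** This stands for capture of events. It does not settle which patients form the denominator of a reported rate. Acute success has no comparable protection.
- **The recruitment-point text under Section 2.4 is redacted and may contain a rule.** This stands, and its absence is not counted against the plan. Section 6, where an analysis denominator would be expected, is readable and gives none.
- **The size and direction come from assumptions.** This stands. A worse outcome in the non-qualifying cases is plausible but not documented.
- **Analysis by devices used is legitimate in a single-arm observational registry.** This stands for the comparison of combinations, so planned combination need not become the primary grouping. Nor need every aborted procedure be counted as a failure by rule while acute success has no criterion.

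**Conclusion.** The point holds in limited form. Section 2.5 states a qualifying condition that is settled only after consent and during the procedure, and the readable plan sets no denominator of all started procedures to offset it. This can leave out a small group: procedures stopped before a second listed type was used, or switched so that fewer than two listed types remained.

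Acute success is the more exposed outcome. The serious-event rate is exposed only if it is computed on qualifying patients.

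The size cannot be determined from the documents. Under the assumed rates in Step 4, 4.0% would be reported where 4.2-6.1% applies over all started procedures. Under those in Step 5, 95% acute success would be reported where 92.2-94.6% applies. Both ranges presume that all non-qualifying cases are lost and do worse; with equal outcomes the bias is nil. Most of the range lies within sampling error at 400 patients. The case for acting rests on the low cost of the change, and on the difficulty of recovering the planned combination reliably afterwards.

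**What to change.** - **Section 2.5:** let consented patients in whom a procedure with a qualifying combination was planned and started remain in the registry, whatever devices were finally used. Define the start by one recorded event, such as introduction of the first listed device.
- **Section 6, main reporting:** report safety and acute success on all started procedures.
- **Section 6, accounting:** tabulate the number, reasons and outcomes of cases that miss the two-type condition, including aborted procedures and switches.
- **Section 6, comparison by combination:** keep the set with two listed types used, and add grouping by planned combination as a sensitivity analysis.

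The cost is wording in two sections and one CRF field for the planned combination, completed before the procedure. A few patients without the full combination enter the denominator, and the reported figures may be slightly less favourable. Clinical care does not change.

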### List of products/devices that should be used in this registration:

[figure not shown]
Combination of at least 2 devices:

- Ablation Catheter: TactiCath or FlexAbility
- Sheathed access: Agilis NxT or Swartz Braided
- Diagnostic catheter: Inquiry Afocus II DL, Optima or Reflexion Spiral

In the case of mapping, EnSite Velocity will need to be used.

Only commercially available SJM products should be used in this registration. The manuals provided should be consulted. New models that are made available in the market can be used once they are available, have ANVISA registration and approved for commercialization.

### 3 Data collection

All procedures will follow the local standard of care

3.2

### 3.2.1 Recruitment & Informed Consent Process

The investigator is responsible for screening for this Registry and obtaining the Informed Consent Form (ICF) from the patient, as applicable in accordance with local regulations. Obtaining the Informed Consent Form is mandatory for all patients (or their legal representatives) prior to participation in the investigation. The process of obtaining the TCLE must comply with the latest version of the Declaration of Helsinki, ISO 14155 and all applicable regulations. The principal investigator will conduct the consent process. This process will include a verbal discussion with the patient about all aspects of the clinical investigation that are relevant to their decision to participate in the study. It is crucial that this discussion is documented (patient hospital records).

The patient will be provided with a Free and Informed Consent Form written in a language that is understandable to the patient and that has been approved by the Ethics Committee. The patient will be given sufficient time to consider participation and ask questions if necessary.

In order to avoid any kind of undue influence, or inducement of the patient to participate, the sponsor requests the investigator to sign the Informed Consent Form only after the patient has signed and dated the document and therefore has voluntarily decided to participate.

The informed consent of a patient should always be dated and signed personally by the patient and the investigator responsible for conducting the informed consent process. It is crucial that the signature of the ICF is documented in the source documents (hospital records of the patient).

One copy of the original ICF must be kept on file by the investigator and a second signed original copy is provided to the research participant (responsibility of the investigator). The patient's legal rights will not be waived, nor will they appear to be unenforced. Native non-technical language will be used, understandable to the patient. New important information that becomes available during registration will need to be

provided in writing to new and existing patients. If relevant, all affected patients should confirm

Page 11 from 21

their participation in the study by providing their written informed consent.

### 3.2.2 Initial Data

The following information will be collected:

- Patient demographics;
- History of Atrial Fibrillation (type, frequency, duration and other arrhythmias besides AF);
- Cardiovascular history (NYHA class, AE diameter, LVEF% and grade of valvular heart disease);
- Medical history (pre-existing conditions and cardiac procedures).

### 3.2.3 Ablation Procedure

- Products/Devices used;
- Ablation Parameters;
- Definition of ablation success and outcome;
- *User feedback* (Combination of products chosen, product handling, ease of use in combination with other equipment);
- Number, experience and type of service;
- Definition of the standard of care (follow-up procedures and occurrences).

### 3.2.4 6 and 12 Months of Follow-up (+/- 30 days)

- Recurrence of atrial arrhythmias: list of atrial arrhythmias since the last visit, classification of episodes, duration of episodes (only events with evidence of source data should be recorded)
- Changes in therapy (new antiarrhythmic drug, redone procedures).
  
- In case of repetition of procedures, reconnections and new ablations should be documented.

### 3.2.5 Serious cardiovascular adverse events

An adverse event should be reported in this registry when the event is considered to be of cardiovascular origin and has the potential to lead to:

-Death

- A serious deterioration of the patient's health , which may result in:

- A life-threatening disease or condition

- In: permanent capacity of a body structure or a bodily function;

- Prolonged hospitalization

- Medical or surgical intervention to prevent life-threatening disease or injury

- Malignant tumor

- Fetal distress, fetal death, or a congenital abnormality or defect

Planned hospitalization for a pre-existing condition is not considered a serious adverse event.

Cardiovascular serious adverse events (CAEs) include, but are not limited to, the following:

abnormal ECG, angina (chest pain), arrhythmia, fistula, complete heart block, coronary artery injury, cardiac perforation, thromboembolism, fluid overload, damage to components of the ICD or implantable pacemaker, morte, displacement of implantable defibrillator, and endocarditis, exacerbation of pre-existing atrial fibrillation, heart failure, arterial hypertension, AV block, esophageal fistula, myocardial infarction, obstruction/perforation/damage of the vascular system, palpitations, cardiac effusion/tamponade, pericardial effusion without tamponade, pericarditis, pulmonary vein dissection,

pulmonary vein stenosis, pulmonary vein thrombus, complete heart block, valvular damage, or ventricular arrhythmia insufficiency requiring defibrillation.

Procedure for the evaluation, registration and notification of EAGs

Cardiovascular EAGs should be reported following local regulation. All cardiovascular EAGs between patient recruitment and the end of registration must be reported to the sponsor and local Ethics Committees in accordance with local regulations.

In the event that an EAG occurs, complete and submit an Adverse Event to St. Jude Medical.

Additional information may be requested, if necessary, by Sponsor in order to report EAGs to regulatory authorities. The investigator must notify the Ethics Committee, if applicable, in accordance with national and local laws and regulations.

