### 6 Statistical Considerations

This is a national, multicenter, post-marketing registry, made on the basis of observations. The purpose of this registry is to evaluate the performance and clinical efficacy of a combination of

SJM ablation products for the treatment of individuals with Atrial Fibrillation (AF), and to collect scientific data in a real-world setting. Up to 400 patients will be enrolled in this registry. As this is a post-marketing study, the sample size adopted was not calculated, however, the selected sample size (up to 400 patients) provides an adequate estimate for the conclusions of the study. Long-term effectiveness as well as procedure efficiency data will be compiled (see section 2.2). Descriptive statistics will be performed to compare the impact of treated medical conditions and the combination of devices used in the procedure and follow-up of clinical evolution. Statistical tests will be applied to determine clinical significance as needed.

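### The serious-event definition in 3.2.5 lists only prolonged hospitalization, while its exemption implies that unplanned admissions count; the text should be reconciled so that centers report alike.

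*Combined protocol and SAP*

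**What the plan says.** Section 3.2.5 requires a report "when the event is considered to be of cardiovascular origin and has the potential to lead to" death or a serious deterioration of health. The forms of deterioration are then listed. Hospitalization appears once, as "Prolonged hospitalization"; a new, initial or unplanned admission does not appear. The nearest other ground is "Medical or surgical intervention to prevent life-threatening disease or injury". The first full sentence after the list reads: "Planned hospitalization for a pre-existing condition is not considered a serious adverse event".

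A list of diagnoses follows, introduced by "Cardiovascular serious adverse events (CAEs) include, but are not limited to, the following". It is long and open-ended. It names pericarditis, pericardial effusion without tamponade, arrhythmia, angina and heart failure, and also palpitations, abnormal ECG and arterial hypertension.

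Section 3.2.4 gives the 6- and 12-month items: recurrence of atrial arrhythmias, changes in therapy, and repeat procedures. Hospital admission is not among them. The first goal in section 2.2 is "Ensure patient safety as part of after-sales surveillance".

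**The concern.** Whether a patient was admitted is a fact that every center can record in the same way. Whether an event could have become life-threatening, or whether an intervention averted that, is a judgement. By naming only prolonged hospitalization, the list drops the observable ground and leaves the judged ones. The exemption that follows is written as if the observable ground were present.

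One center can therefore take the list literally and file no form for a short unplanned readmission, while another takes the exemption as its guide and files one. The serious-event count then partly reflects how each center reads the section. This matters for surveillance. It also matters for section 6, which plans descriptive comparisons by the combination of devices used: if the choice of devices differs between centers, differences in reporting could pass for differences between combinations.

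**Working it through.** No figure in the plan is tied to this definition, so the check sets the parts of 3.2.5 side by side and applies them to typical cases.

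| Case | Hospitalization item, read literally | Implied by the exemption | Named list |
|---|---|---|---|
| Index stay extended by a cardiovascular complication | Met | Counts | Depends on diagnosis |
| Discharged, then a short unplanned readmission with pericarditis | Not met | Counts | Named |
| Discharged, then a short unplanned readmission with a diagnosis not on the list, such as syncope | Not met | Counts | Not named, though the list is open |
| Planned admission for a pre-existing condition | Not met | Exempt | Does not arise |
| Palpitations without admission | Not met | Does not arise | Named |

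**Rows 2 and 3** show the mismatch: the item and the exemption give opposite answers for a short unplanned readmission. Row 4 shows why the exemption looks misplaced. If only prolongation counted, a planned admission of normal length would need no exemption.

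**Rows 2 and 5** show that the named list does not settle the matter, because it can be read in two ways.
- If a named diagnosis is serious by name, row 2 is reported. So is row 5, and the criteria become redundant for every named diagnosis.
- If the list only illustrates events that must also meet a criterion, row 5 drops out. Row 2 then depends on whether the investigator sees potential for a listed outcome.

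The section does not say which reading applies.

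**Row 3** depends on the investigator's judgement under either reading.

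**Scale.** Section 6 gives up to 400 patients and states that "the sample size adopted was not calculated"; no admission or event rate appears anywhere. Only the weight of a single unreported patient can be computed, taking full enrolment and the approximately 25 centers of section 2.3:
- Overall: 1/400 = 0.25 percentage points.
- Average center size: 400/25 = 16 patients.
- Within an average center: 1/16 = 6.25 percentage points.

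A few unreported patients would move the overall rate little, but a single one moves a center's rate visibly.

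**The case against.** The strongest reply is that 3.2.5 already captures most of what matters. The named list covers most diagnoses likely to bring a patient back after ablation, including pericarditis and effusion without tamponade, and it is open-ended. The threshold is potential rather than outcome, so an event serious enough to readmit a patient may well qualify through another ground. Prolonged can also be read as any long stay, not only an extended index stay. This largely stands, and it limits the practical loss. It does not remove the mismatch: the list's relation to the criteria is unstated, and the potential-based threshold points to outcomes that do not include admission.

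A second reply is that the wording is a translation slip. That is plausible, since the same section has other garbled and untranslated words. But nothing elsewhere in the document corrects it, and this is the text supplied for review. The commitments to ISO 14155 (3.2.1 and 4.5) and to reporting under local regulation (3.2.5) do not resolve it within the document, because no definition from those sources is reproduced.

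A reader might also infer that readmissions are recorded nowhere in the registry. The documents do not support that. The case report forms are not included, the record flowchart listed in the contents is not shown, and 3.2.3 mentions follow-up procedures and occurrences. Readmissions for arrhythmia or a repeat procedure would be at least partly visible through the 3.2.4 items. What can be said is that 3.2.4 lists no admission item.

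**Conclusion.** The point holds as an inconsistency in a stated reporting rule. The hospitalization item leaves out unplanned admission, the exemption presupposes it, and no other section reconciles them. The exposed events are short unplanned cardiovascular admissions: those with unlisted diagnoses under any reading, and those with named diagnoses if the list is only illustrative. For these events the error runs towards undercounting, unevenly between centers.

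The size cannot be stated, because the documents give no admission rate and no split by diagnosis. Given the breadth of the named list and the potential-based threshold, it is probably small. A reader might infer that a large share of serious events would go unreported, or that a late-harm signal would be missed. Neither is supported: any such share would rest on assumed rates, and late complications such as fistula, pulmonary vein stenosis and thromboembolism are named individually. The conclusion rests on two inferences: that the exemption implies other admissions count, and that centers would work from this text.

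**What to change.** In 3.2.5, replace the hospitalization item with: unplanned in-patient hospitalization or prolongation of an existing hospitalization. Keep the exemption for planned admission for a pre-existing condition; it then has something to exempt. Add one sentence stating whether diagnoses on the named list are reportable by name or only when a listed criterion is also met.

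Check the 6- and 12-month forms. If they do not already record unplanned admissions, add one yes/no item covering the period since the last visit, with date and reason. That would allow event reports to be checked against admissions during centralized data review (4.3).

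The cost is two edits to one section and at most one question per follow-up visit. The downside is a few more event forms and a slightly higher reported serious-event rate. The change affects reporting only, not patient care.
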